### 5.2.4 Populations Used in Analyses

Baseline and demographic analyses will be performed on all enrolled subjects.

The safety analyses will be performed on the Safety Analysis Set.

The immunogenicity analyses will be performed on both the FAS and PPAS.

---

a for which safety data are scheduled to be collected.

## 5.3 Handling of Missing Data and Outliers

### 5.3.1 Safety

In all subject listings, partial and missing data will be clearly indicated as missing. No search for outliers will be performed.

#### 5.3.1.1 Immediate

For unsolicited non-serious systemic AEs, a missing response to the “Immediate” field is assumed to have occurred after the 20-minute surveillance period and will not be imputed.

#### 5.3.1.2 Causality

Unsolicited AEs and SAEs with missing causality will be considered as related to vaccination.

#### 5.3.1.3 Measurements

Missing measurements (for temperature or length) will remain missing and will not be imputed. Nevertheless, the following rule will be applied: If the measurement (temperature or length) is missing the value after the decimal point, the data will be analyzed by replacing “MD” with zero. For example, a “102.MD°F” daily temperature will be considered as “102.0°F” during the analysis.

#### 5.3.1.4 Intensity

No replacement of the missing qualifier will be done. For analysis, the missing class for the AE qualifier will be provided in the descriptive tables.

#### 5.3.1.5 Start Date and Stop Date

No replacement of missing dates will be performed.

For instance:

- If the onset of an AE cannot be calculated due to a missing start date, then the onset will be considered as missing
- If the stop date of an unsolicited AE is missing, then the duration of that AE will be considered as missing
- If the stop date of a solicited reaction continuing after the solicited period is missing or incomplete, then the number of days of occurrence of that solicited event will be considered as missing

All missing and partially missing dates will be listed where appropriate.

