9.3.1.3.2 Reactogenicity (Solicited Reactions From Day 0 Through Day 7 After Each Vaccination)

After each vaccination, subjects or subject's parent/guardian will be provided with a safety diary card, a digital thermometer, and a flexible ruler, and will be instructed how to use them. The following items will be recorded by the subjects in the diary card on the day of vaccination and for the next 7 days (i.e., Day 0 through Day 7) until resolution:

- Daily temperature, with the route by which it was taken
- Daily measurement or intensity grade of all other solicited injection site and systemic reactions
- Action taken for each event, if any (e.g., medication)

The action taken by the subject or subject's parent/guardian to treat any **solicited reactions** will be classified in the eCRF using the following scale:

0: None

1: Medication (self-medication with an existing prescription or over-the-counter medication)

2: Health care provider contact (no new medication prescribed)

- 3: Health care provider contact and prescription of a new medication (health care provider instructed subject to take a new medication, either an over-the-counter medication or one requiring a written prescription)
- 4: Hospitalization (inpatient)

Subjects or subject's parent/guardian will be contacted by telephone 8 days after each vaccination to remind them to record all safety information in the diary card.

If the timing of the telephone call should fall on a weekend or a holiday, the call should be made on the next business day. If contact is not made on the designated day, study staff will continue calling until contact is made. Every telephone attempt and its outcome will be documented in the source document.

Table 9.1, Table 9.2, Table 9.3, Table 9.4, and Table 9.5 present the injection site reactions and systemic reactions that are prelisted in the diary cards and eCRF, together with the intensity scales.

Table 9.1: Solicited Injection Site Reactions: Terminology, Definitions, and Intensity Scales (Subjects 6 to < 36 Months of Age)

CRF term (MedDRA lowest level term [LLT])	Injection site tenderness	Injection site erythema	Injection site swelling
Diary card term	Tenderness	Redness	Swelling

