#### 4.4.1.1.5 Number of Days of Occurrence

Number of days of occurrence during the period considered will be derived from the daily intensities computed as described in Section 4.4.1.1.1. It corresponds to the number of days with daily intensities of Grade 1, Grade 2, or Grade 3. The number of days of occurrence during the solicited period with a specified intensity may also be derived. For subjects who received 2 doses, the worst-case scenario will be used for the post-any dose summary (i.e., the larger number of days will be used if present for both doses, or the available number of days will be used if present for either dose).

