#### 4.4.1.1.6 Overall Number of Days of Occurrence

If a reaction is ongoing at the end of the solicited period, then the overall number of days of occurrence will be derived from the daily intensities and the stop date of the reaction after the end of the solicited period. The overall number of days of occurrence will be:

$$(\text{stop date} - \text{last vaccination date}) + (\text{number of days of occurrence within the solicited period}) - \text{length of the solicited period} + 1$$

If the stop date is missing or incomplete (contains MD), the overall number of days of occurrence will be considered as Missing. For subjects who received 2 doses, the worst-case scenario will be used for the post-any dose summary (i.e., the larger number of days will be used if present for both doses, or the available number of days will be used if present for either dose).

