#### 4.4.1.1.7 Ongoing

Ongoing will be derived from the last daily intensity of the solicited period computed as described in Section 4.4.1.1.1 and the maximum intensity during the ongoing period. The Investigator's ongoing flag is not used because the measurement would determine the ongoing status of the reaction.

If the last daily intensity of the solicited period is at least Grade 1 and the maximum intensity in the ongoing period is also at least Grade 1, then the reaction is considered ongoing. In all other cases, the reaction will not be considered as ongoing.

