#### *Solicited reactions*

The solicited injection site reactions and the solicited systemic reactions will be presented separately (except in summary tables).

Solicited reactions will be presented according to their nature (MedDRA [the latest version at database lock] PT), intensity (Grade 1, 2, or 3), time to onset, and number of days of occurrence.

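### SAP 5.3.1.5 sets the wrong duration variable to missing when a stop date is absent, and the two-dose worst-case rule can report too few days

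*SAP*

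**What the plan says.** The SAP defines two duration variables for solicited reactions.

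- **Number of days of occurrence (4.4.1.1.5).** "It corresponds to the number of days with daily intensities of Grade 1, Grade 2, or Grade 3". No stop date enters.
- **Overall number of days of occurrence (4.4.1.1.6).** For a reaction ongoing at the end of the solicited period, this adds the days up to the stop date. "If the stop date is missing or incomplete (contains MD), the overall number of days of occurrence will be considered as Missing".

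Both sections have a worst-case rule for the post-any-dose summary of two-dose subjects: the larger value if both doses have one, "or the available number of days will be used if present for either dose".

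Section 5.3.1.5 repeats the missing-date rule but omits the word *overall*: "then the number of days of occurrence of that solicited event will be considered as missing". Section 5.1.3.1 says solicited reactions are presented by "intensity (Grade 1, 2, or 3), time to onset, and number of days of occurrence", and safety endpoints 2 and 3 (SAP 4.3.1.2) also name the number of days of occurrence.

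Section 4.4.1.1.7 decides which reactions are ongoing. It requires at least Grade 1 on the last solicited day and at least Grade 1 afterwards. "In all other cases, the reaction will not be considered as ongoing".

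**The concern.** There are two faults, and the second remains if the first is only a slip of wording.

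1. Sections 5.3.1.5 and 4.4.1.1.5 give different answers for the same named variable. That variable is a stated endpoint and the duration measure the SAP says it will present. Nothing in the SAP says which section prevails, so a programmer could discard a complete Day 0–7 count because of a date that the count does not use.

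2. Under 4.4.1.1.6 itself, a reaction known to have outlasted Day 7 is treated as having no duration information. For a two-dose child, the other dose's value takes its place and is presented as the worst case. For everyone else the value is lost. Only reactions persisting past Day 7 can be lost this way, so the loss is not random with respect to duration.

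**Working it through.** The plan states no figure on this point, so the check applies its rules to cases.

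**Inputs**
- The solicited period is Day 0 through Day 7 (Protocol 9.3.1.3.2: "for the next 7 days (i.e., Day 0 through Day 7) until resolution"), so its length is 8 daily records.
- Overall days (SAP 4.4.1.1.6) = (stop date − vaccination date) + days within the period − length + 1.
- Check of the length: a continuous Day 0–10 reaction gives 10 + 8 − 8 + 1 = 11, which is correct. A length of 7 would give 12.
- Assumption: a reaction that is not ongoing keeps its within-period count as its overall value. The SAP gives the formula only for ongoing reactions.

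**Lower bound when the stop date is missing.** An ongoing reaction stops on Day 8 at the earliest. Overall days are therefore at least 8 + n − 8 + 1 = n + 1, where n is the within-period count.

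**Two-dose example.** Dose 1: pain on 2 days. Dose 2: pain graded on all 8 days, still graded afterwards, no stop date.
- Number of days under 4.4.1.1.5: max(2, 8) = 8.
- Number of days if 5.3.1.5 is applied literally: dose 2 is missing, so 2.
- Overall days under 4.4.1.1.6: dose 2 is missing, so 2, although dose 2 is known to have lasted at least 8 + 1 = 9.

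**The fallback is not always shorter.** Suppose dose 1 starts on Day 7 and truly ends on Day 8, with the stop date missing: 8 + 1 − 8 + 1 = 2 days. If dose 2 lasted 5 days, the reported 5 is the true maximum.

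**How often it would be shorter.** This is an illustration, because the documents give no distribution. One dose is continuous with onset Day 0–7 and true stop Day 8–14 (8 × 7 = 56 patterns). The other is continuous within Day 0–7 (36 patterns). All 56 × 36 = 2016 combinations are weighted equally. The substituted value is:
- shorter in 1806 (89.6%);
- equal in 84 (4.2%);
- longer in 126 (6.2%).

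**One-dose subjects and per-dose tables.** As an illustration, assume 20 subjects with a reaction: 17 lasting 2 days and 3 lasting 11 days.

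| Long reactions without a stop date | Mean days | Share over 8 days |
|---|---|---|
| 0 | (34 + 33)/20 = 3.35 | 3/20 = 15% |
| 1 | (34 + 22)/19 = 2.95 | 2/19 = 10.5% |
| 2 | (34 + 11)/18 = 2.50 | 1/18 = 5.6% |
| 3 | 34/17 = 2.00 | 0/17 = 0% |

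The direction follows from the rule. The size depends entirely on how many stop dates are missing.

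**The case against.** The strongest reply is that 5.3.1.5 is only shorthand. Its rule is one of a list of examples about missing dates, and its trigger matches 4.4.1.1.6, where the overall variable is named. On that reading the conflict is one missing word, the Day 0–7 endpoint is intact, and the example gives 8 days. This is a plausible reading, but the SAP does not state it, and it leaves the two-dose fallback as it is.

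The second reply is that cases should be few. Diary recording runs until resolution. Injection site reactions and solicited systemic reactions are related by convention (Protocol 9.3.1.3.6), and stop dates of all related events are actively sought (footnote to Protocol 9.3.1.3.3, in the section on unsolicited events). Missing dates are also to be listed. This stands as a limit on size. The same footnote treats events without a stop date as ongoing at the end of the study, and the SAP provides no matching class for duration.

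A reader might infer more than the documents support:
- **That the longest reactions drop out.** Long reactions with a stop date stay in, and a short reaction that starts on Day 6 or 7 and runs on without a stop date is affected.
- **That every reaction of 8 or more days without a stop date is lost.** If the later intensity is also missing, 4.4.1.1.7 classes the reaction as not ongoing, and the count of 8 stands.
- **That 4.4.1.1.7 makes the loss worse.** It is a separate mechanism: it may truncate a duration but does not set it to missing. The SAP also gives its reason for setting the Investigator's flag aside, namely that the measurement determines the status.

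**Conclusion.** The concern holds in a limited form. Section 5.3.1.5 conflicts with 4.4.1.1.5 and 4.4.1.1.6, and taken literally it removes an observed endpoint value. Independently of that, the worst-case rule can report too low an overall duration.

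The substitution reaches only children who receive two doses, only the post-any-dose summary, and only when the other dose has a value. Elsewhere the value is simply missing, which can remove only reactions persisting past Day 7. The 89.6% figure rests on equal weighting of assumed patterns and is not a forecast. How many subjects are affected cannot be derived from the documents.

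The consequence is confined to descriptive duration summaries in a study that tests no hypotheses. It is still worth correcting, because describing safety is a study objective, duration is a named component of two endpoints, and the present rule can attach a wrong number to a worst-case label.

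**What to change.** 1. In SAP 5.3.1.5, name the overall number of days of occurrence as the variable set aside, and state that the Day 0–7 count from daily grades is always kept.
2. In SAP 4.4.1.1.6, where a reaction is ongoing under 4.4.1.1.7 and its stop date is missing or incomplete, report overall days in a censored class with the known lower bound: within-period count + 1.
3. In the two-dose rule for overall days, take the maximum of that lower bound and the other dose's value, and report it as ≥. The example becomes max(9, 2), reported as ≥ 9. The counterexample becomes max(2, 5), reported as ≥ 5. Treating the censored dose as automatically the larger would report ≥ 2 there and discard the known 5.
4. Leave 4.4.1.1.7 unchanged.

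The cost is SAP wording and one extra table category. No new data are needed.

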### **5.3.2 Immunogenicity**

For the computations, LLOQ and ULOQ will be managed as follows:

If a titer is < LLOQ, then LLOQ/2 will be used.

If a titer is  $\geq$  LLOQ and < ULOQ, then the titer itself will be used.

If a titer is  $\geq$  ULOQ, then ULOQ will be used.

Missing data will not be imputed. No search for outliers will be performed.

### **5.4 Interim/Preliminary Analysis**

No interim analyses are planned.

### **5.5 Determination of Sample Size and Power Calculation**

The study will enroll approximately 240 subjects: approximately 60 subjects 6 to < 36 months of age will be administered Fluzone Quadrivalent vaccine (Group 1), approximately 60 subjects 3 to < 9 years of age will be administered Fluzone Quadrivalent vaccine (Group 2), approximately 60 subjects 18 to < 65 years of age will be administered Fluzone Quadrivalent vaccine (Group 3), and approximately 60 subjects  $\geq$  65 years of age will be administered Fluzone High-Dose vaccine (Group 4).

No study power was calculated for this study. All analyses will be descriptive.

### **5.6 Data Review for Statistical Purposes**

A review of the data is anticipated through the data review process led by Clinical Data Management before database lock.

### **5.7 Changes in the Conduct of the Trial or Planned Analyses**

Not applicable.

